### 6.1 Subject Enrollment

Subjects will be considered enrolled into the FlexNav study after completion of all of the following steps:

1. Signed informed consent is obtained.
2. Based on the screening assessments, it is determined that the subject meets all of the inclusion and none of the exclusion criteria.
3. Subject is approved by the Subject Selection Committee.
4. Subject assignment (roll-in or analysis) has been determined by the Sponsor.
5. The Portico delivery system enters the subjects' body.

Subjects who are approved by the Subject Selection Committee to receive a Portico valve via transfemoral access and are found during the procedure not to be suitable for this delivery modality (per the heart team medical decision) may receive a Portico valve using an alternate access modality and vice versa. This will be considered a protocol deviation unless the Subject Selection Committee pre-approved the subject for multiple access sites. The rationale for this decision must be documented by the site.

## 6.2 Roll-in Cohort

A minimum of one (1) and up to three (3) roll-in subjects will be required per primary implanting physician at each site. Data from roll-in subjects will be added to the IDE Roll-in Registry and will not be included in the analysis population of 100 subjects. A maximum of 100 roll-in subjects will be permitted in the study.

The total number of roll-in subjects required per site will be at the discretion of the Sponsor and will be based on the primary implanting physician's recent Portico implant experience.

[REDACTED]

## 6.3 Proctoring

[REDACTED]

## 7. STUDY CONDUCT

Assessments required at screening, baseline, pre- and post-procedure, prior to hospital discharge and during follow-up in the FlexNav study will be the same as that in the pivotal IDE trial. Stroke ascertainment and evaluation will be performed according to VARC II recommendations and the pivotal IDE protocol. Detailed information can be found in Section 7.0 of the main protocol.

Subjects enrolled in the FlexNav study will be followed for a minimum of one year and annually thereafter for up to 5 years.

### 7.1 Core Laboratories

[REDACTED] independent core laboratories and processes used in the pivotal IDE trial will be utilized for evaluating CT images, ECG rhythms and echocardiograms for the FlexNav study.

### 7.2 Subject Selection Committee

The independent Subject Selection Committee will be responsible for final approval of a study subjects':

1. risk classification (high vs extreme) based on patients' clinical history, STS score, non-STs comorbidities (including frailty indices) and key patient demographics.

[REDACTED]

2. primary access route based on independent core-laboratory CT imaging. A secondary access route may also be approved.

As in the pivotal IDE trial, the Subject Selection Committee will provide guidance with respect to Portico valve size selection based on CT-measured annular dimensions (area, perimeter, diameter, eccentricity) and calcification. However, the investigational site has the final decision for which Portico valve size is selected for implantation.

## **8. DATA COLLECTION AND MANAGEMENT**

The schedule for data collection and management of data will follow the pivotal IDE trial. Refer to Section 8.0 of the main protocol for details.

Enrolled subjects who undergo a Portico implant attempt but do not receive a Portico valve will be assessed for any adverse events through to 30 days post-procedure, and will then be terminated from the study.

If a subject is consented and undergoes study-specific testing (i.e., testing that would not be done if they were not being considered for the study) but is not enrolled in the study (FlexNav™ Delivery System does not enter the subject's body), the subject will be exited from the study without any further follow-up.

## **9. INDEPENDENT BOARDS**

### **9.1 Clinical Events Committee**

All adverse events will be adjudicated by the same independent Clinical Events Committee used in the pivotal IDE trial according to the Valve Academic Research Consortium (VARC II) definitions. The independent Clinical Events Committee will have final adjudication responsibilities for subject outcomes related to the primary safety endpoint at 30 days and descriptive endpoints at 30 days and one-year follow-up.

The independent Clinical Events Committee will be responsible for adjudicating the following adverse events at 30 days:

- mortality (all-cause and cardiovascular related)
- stroke (non-disabling and disabling)
- life-threatening bleeding requiring blood transfusion
- major bleeding
- acute kidney injury requiring dialysis
- major vascular complications (access-site related and access related)
- minor vascular complications
- permanent pacemaker insertion

The independent Clinical Events Committee will be responsible for adjudicating the following adverse events at one year:

- mortality (all-cause and cardiovascular related)

### 10.3 Primary Endpoint

Acceptable safety of the FlexNav™ Delivery System will be determined from a predefined precision estimate for VARC II-defined major vascular complications at 30 days. Results will be summarized and descriptively compared in context of results for the first-generation Delivery System in the randomized cohort (Portico arm) of the pivotal IDE trial.

A comparison to published results for the Portico valve and latest-generation commercially- available transcatheter valves will also be provided.

### 10.4 Descriptive Endpoints

Descriptive endpoints will be summarized and presented for the analysis population (n=100 subjects) and according to access route (transfemoral vs alternative access). Additionally, all descriptive endpoints at 30 days will be summarized and descriptively compared to rates reported in the randomized cohort of the pivotal IDE trial as well as published results for Portico and latest-generation commercially available valves.

[Redacted]

[Redacted]

[Redacted]

[Redacted]

[Redacted]

[Redacted]

[Redacted]

[Redacted]

[Redacted]

[Redacted]

[Redacted]

[Redacted]

[Redacted]

[Redacted text block]

[Redacted text block]

[Redacted text block]

[Redacted text block]

[Redacted text block]

[Redacted text block]

[Redacted text block]

[Redacted text block]

[Redacted text block]

[REDACTED]

[REDACTED]

[REDACTED]

[REDACTED]

[REDACTED]

[REDACTED]

[REDACTED]

[REDACTED]

[REDACTED]

[REDACTED]

[REDACTED]

[REDACTED]

[REDACTED]

[REDACTED]

[REDACTED]

[REDACTED]

[REDACTED]

[REDACTED]

[REDACTED]

[REDACTED]

[REDACTED]

[REDACTED]

[REDACTED]

[REDACTED]

[REDACTED]

[REDACTED]

[figure not shown]
[figure not shown]
[Redacted text block]

[Redacted text block]

[Redacted text block]

[Redacted text block]

[Redacted text block]

[Redacted text block]

[Redacted text block]

[Redacted text block]

[Redacted text block]

[Redacted text block]

[REDACTED]

[REDACTED]

[REDACTED]

[REDACTED]

[REDACTED]

[REDACTED]

[REDACTED]

[REDACTED]

[REDACTED]

[REDACTED]

[REDACTED]

[REDACTED]

[REDACTED]

[REDACTED]

[REDACTED]

[REDACTED]

[REDACTED]

[REDACTED]

[REDACTED]

[REDACTED]

[REDACTED]

[REDACTED]

[REDACTED]

[REDACTED]

[REDACTED]

[REDACTED]

[REDACTED]

[REDACTED]

[REDACTED]

[REDACTED]

[REDACTED]

[REDACTED]

[REDACTED]

[REDACTED]

[REDACTED]

[REDACTED]

[REDACTED]

[REDACTED]

[Redacted text block]

[Redacted text block]

[Redacted text block]

[Redacted text block]

[Redacted text block]

[Redacted text block]

[Redacted text block]

[Redacted text block]

[Redacted text block]

[Redacted text block]

[Redacted text block]

[Redacted text block]

[Redacted text block]

[Redacted text block]

[Redacted text block]

[Redacted text block]

[Redacted text block]

[Redacted text block]

[Redacted text block]

[REDACTED]

[REDACTED]

[REDACTED]

[REDACTED]

[REDACTED]

[REDACTED]

[REDACTED]

[REDACTED]

[REDACTED]

[REDACTED]

[REDACTED]

[REDACTED]

The objective of this clinical trial is to evaluate the safety and effectiveness of the SJM Portico Transcatheter Heart Valve and Delivery Systems (Portico) via transfemoral and alternative delivery methods. The Portico™ Transcatheter Heart Valve is indicated for patients with symptomatic severe native aortic stenosis, who are considered high or extreme surgical risk. [REDACTED], an additional study arm (“FlexNav study” or “FlexNav cohort”) has been added to the pivotal IDE trial. The objective of the FlexNav study is to characterize the safety of the second-generation Portico Delivery System (“FlexNav™ Delivery System”).

1.3 **Clinical Investigation Design**

The pivotal IDE trial is a prospective, multi-center, randomized, controlled clinical trial, designed to evaluate the safety and effectiveness of the SJM Portico Transcatheter Heart Valve and Delivery Systems (Portico) via transfemoral and alternative delivery methods. The pivotal IDE trial includes a randomized cohort of 750 patients that will be used to support a Premarket Approval (PMA) application for the Portico™ Transcatheter Aortic Heart Valve in the United States. This trial includes both high-risk and extreme-risk patients. Prior to randomization, patients will be classified as high or extreme risk and stratified by vascular access within each risk group. At the time of the primary analysis, the risk cohorts will be combined.

The FlexNav study will be conducted as a prospective, multicenter, investigational study arm of the pivotal IDE trial. Thirty-day outcomes data from the 100 subjects in FlexNav study will be used to support the PMA application for the Portico™ Transcatheter Aortic Heart Valve and the FlexNav™ Delivery System.

1.4 **Endpoints**

1.4.1 **Pivotal IDE Endpoints (Randomized cohort)**

Primary Safety Endpoint

Non-hierarchical composite of all-cause mortality, disabling stroke, life threatening bleeding requiring blood transfusion, acute kidney injury requiring dialysis, or major vascular complications at 30 days.

Primary Effectiveness Endpoint

A composite of all-cause mortality or disabling stroke at one year.

Statistical Analysis Plan

Secondary Endpoints

1. Severe aortic regurgitation (AR) at one year
2. Kansas City Cardiomyopathy Questionnaire (KCCQ) at one year
3. Moderate or severe aortic regurgitation at one year
4. Six-minute walk at one year

Descriptive Endpoints

1. Acute device success defined as:
 - o Absence of procedural mortality AND
 - o Correct positioning of a single prosthetic heart valve into the proper anatomical location AND
 - o Intended performance of the prosthetic heart valve (mean aortic valve gradient <20 mmHg or peak velocity <3 m/s, no moderate or severe prosthetic valve regurgitation) AND
 - o Successful access was obtained as intended by group assignment
2. Kansas City Cardiomyopathy Questionnaire (KCCQ) at one year for Centers for Medicare and Medicaid Services (CMS) National Coverage Decision primary quality of life endpoint
3. Major vascular complications at 30 days from the index procedure
4. NYHA functional classification at 30 days, 6 months, and one year
5. Six-minute walk test at 30 days, 6 months, and one year
6. Paravalvular Leak (PVL) at 30 days, 6 months, and one year
7. Aortic insufficiency greater than trace at 30 days, 6 months, one year, and two years
8. Reintervention to treat aortic insufficiency at 1 year and 2 years
9. Permanent pacemaker insertion at 30 days from the index procedure
10. Major bleeding at 30 days from the index procedure
11. Acute kidney injury at 30 days from the index procedure
12. Individual components of the primary effectiveness endpoint
 - o All-cause mortality at 30 days, 6 months, one year and two years
 - o Disabling stroke at 30 days, 6 months, one year and two years
13. Non-disabling Stroke and Transient Ischemic Attack (TIA) at 30 days, 6 months, one year, and two years
14. Atrial fibrillation at one year and two years
15. Quality of Life (QOL) from baseline to 30 days, 6 months and one year

1.4.2 FlexNav Study Endpoints

Primary Safety Endpoint:

VARC II defined major vascular complication rate at 30 days.

Descriptive Endpoints:

1. Non-hierarchical composite of all-cause mortality, disabling stroke, life threatening bleeding requiring blood transfusion, acute kidney injury requiring dialysis, or major vascular complications at 30 days from the index procedure
2. All-cause mortality at 30 days and one year from the index procedure
3. Disabling stroke at 30 days and one year from the index procedure

Statistical Analysis Plan

4. Non-disabling stroke at 30 days from the index procedure
5. Life threatening bleeding requiring blood transfusion at 30 days from the index procedure
6. Major bleeding at 30 days from the index procedure
7. Acute kidney injury at 30 days from the index procedure
8. Minor vascular complication rates at 30 days from the index procedure
9. Permanent pacemaker insertion at 30 days from the index procedure
10. Paravalvular Leak (PVL) at 30 days from the index procedure
11. NYHA functional classification at 30 days from the index procedure
12. KCCQ Quality of Life score from baseline to 30 days from the index procedure
13. Technical device success defined as successful vascular access, delivery and deployment of the Portico Valve; retrieval with the delivery system and correct positioning of a single valve in the proper anatomical location
14. Composite of all-cause mortality or disabling stroke at one year from the index procedure

1.5 Randomization (Randomized cohort)

Subjects will be randomized per 1:1 ratio to test (Portico) vs. commercially available valve (CAV). group according to a computer-generated randomization scheme. [REDACTED]

1.6 Blinding

Subjects were not blinded to their assigned treatment. Packaging and design of the Portico and CAVs are different, and thus, implanters were not blinded to the assigned treatment. There was no randomization or blinding of treatment in the FlexNav cohort.

2.0 ANALYSIS CONSIDERATIONS

2.1 Analysis Populations

The primary analysis for the randomized cohort will be based on the intention-to-treat (ITT) population. In addition, results were summarized for the As Treated and Per Protocol populations. The definitions of these analysis populations are defined below.

Statistical Analysis Plan

In the FlexNav cohort, the analysis population included all subjects in whom an Portico valve implant was attempted [REDACTED]

2.2 Statistical Methods

2.2.1 Descriptive Statistics for Continuous Variables

For continuous variables, results will be summarized with the numbers of observations, means, and standard deviations, and in addition, with medians, quartiles, minimums, maximums, and 95% confidence intervals for the means, when specified.

2.2.2 Descriptive Statistics for Categorical Variables

For categorical variables, results will be reported as frequencies with percentages and were compared using chi-square tests or two-tailed Fisher's exact test.

2.2.3 Descriptive Statistics for Time-to-event Variables

Time-to-event analyses will be performed using the Kaplan-Meier method and all comparisons were made using the log-rank test.

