**11.7.4 Analysis of Descriptive Endpoints**

The descriptive endpoints listed in section 1.3 will be summarized using descriptive statistics including mean, standard deviation, median and range for continuous data and count and percentage for categorical data.

[Redacted text block]

[Redacted text block]

[Redacted text block]

[Redacted text block]

[Redacted text block]

[REDACTED]

[REDACTED]

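### SAP 2.2.3 does not separate fatal from non-fatal outcomes: Kaplan-Meier with deaths censored would overstate one- and two-year risks of four descriptive endpoints, and Protocol 11.7.4 names a different summary for them

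*SAP*

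**What the plan says.** SAP 2.2.3 consists of one sentence: "Time-to-event analyses will be performed using the Kaplan-Meier method and all comparisons were made using the log-rank test". The readable text does not list which endpoints count as time-to-event, does not say what happens to a subject who dies before a non-fatal event, and names no competing-risk estimator.

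Four descriptive endpoints in SAP 1.4.1 (repeated in Protocol 1.3.1) are dated non-fatal events that death can prevent:

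- "Disabling stroke at 30 days, 6 months, one year and two years"
- "Non-disabling Stroke and Transient Ischemic Attack (TIA) at 30 days, 6 months, one year, and two years"
- "Atrial fibrillation at one year and two years"
- "Reintervention to treat aortic insufficiency at 1 year and 2 years"

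Other text points to a different summary. Protocol 11.7.4 says that the descriptive endpoints will be "summarized using descriptive statistics including mean, standard deviation, median and range for continuous data and count and percentage for categorical data". For categorical variables, SAP 2.2.2 says that "results will be reported as frequencies with percentages and were compared using chi-square tests or two-tailed Fisher's exact test".

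The primary effectiveness endpoint is not in question, because death is part of it: "A composite of all-cause mortality or disabling stroke at one year". The primary safety endpoint is a 30-day composite that also contains death.

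**The concern.** Kaplan-Meier treats a censored subject as still able to have the event later. A subject who has died cannot. If deaths are censored, one minus the Kaplan-Meier estimate answers a hypothetical question (the risk if nobody died first) and lies above the proportion of patients who actually have the event. In a population at high or extreme surgical risk followed for two years, death before a stroke or a reintervention will not be rare.

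The documents also leave two methods open for the same endpoints. SAP 2.2.3 naturally covers a dated event, while Protocol 11.7.4 and SAP 2.2.2 give simple percentages. No readable sentence chooses between them. At two years the two can give visibly different rates, and SAP 1.6 states that subjects and implanters were not blinded. The choice is therefore better fixed in advance.

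At stake are the absolute one- and two-year rates of stroke, atrial fibrillation and reintervention that a reader would use to describe the valve. The success decision is not at stake.

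**Working it through.** **Inputs.** The plan states no figure for this point, so there is none to reproduce. It gives no readable post-implant mortality or event rate either. Every rate below is an assumption, shown as a range. That Kaplan-Meier would censor deaths is also an assumption; it is the usual practice but is not written in the SAP.

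**Model.** Let the non-fatal event have constant hazard *l* and death have constant, independent hazard *m*, with mortality *D* by time *t*.

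- *m* = −ln(1 − *D*)/*t*
- True cumulative incidence: *C* = *l*/(*l* + *m*) × [1 − exp(−(*l* + *m*)*t*)]
- One minus Kaplan-Meier, deaths censored: *K* = 1 − exp(−*l t*)

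Fix *C* and *D*, solve for *l*, and compare *K* with *C*.

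**Worked case: *C* = 5% at two years, *D* = 30%.**

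- *m* = −ln(0.70)/2 = 0.1783
- *l* = 0.0306 solves the equation: 0.0306/0.2089 × [1 − exp(−0.4179)] = 0.0500
- *K* = 1 − exp(−0.0612) = 5.93%, a ratio of 1.19

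With the same mortality, a true 12% would show as 14.2%.

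**Range under constant hazards.**

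| Mortality by the time point | True 5% shows as | Relative excess |
|---|---|---|
| 15% | 5.41% | 8% |
| 20% | 5.57% | 11% |
| 25% | 5.75% | 15% |
| 30% | 5.93% | 19% |
| 35% | 6.14% | 23% |
| 40% | 6.37% | 27% |

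For a true 10%, the figures are 10.8%, 11.5% and 12.7% at 15%, 25% and 40% mortality.

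**If events cluster around the procedure.** Use two stages. Stage 1 is the first 30 days, with a share *s* of the events and mortality *d*; the formulas above give *K*₁. The fraction alive and event-free is then *S*₁ = (1 − *K*₁)(1 − *d*). Stage 2 has mortality 1 − (1 − *D*)/(1 − *d*) and incidence (1 − *s*)*C*/*S*₁, which gives *K*₂. Overall, *K* = 1 − (1 − *K*₁)(1 − *K*₂).

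- *s* = 80%, *d* = 4%, *C* = 5%, *D* = 15%: *K*₁ ≈ 4.08%; *S*₁ ≈ 0.921; stage-2 mortality 11.5%; stage-2 incidence 1.09%; *K*₂ ≈ 1.15%; *K* = 5.19%, an excess of about 4%. With *D* = 25% the result is 5.26%, and with *D* = 40% it is 5.39%, an excess of about 8%.
- *s* = 50%, death hazard constant throughout: excess 7% at one year (20% mortality) and 10% at two years (30% mortality). The upper end is soft: setting *d* to 4% moves these to 8% and 12%.

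**At 30 days.** With 2–5% mortality, a true 5% becomes 5.05–5.13%.

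**Composites and mortality.** Death counts as an event, so it is not censored and this bias does not arise.

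**Comparison between arms.** Take the same event hazard in both arms (*l* = 0.0306) and two-year mortality of 25% in one arm and 35% in the other (*m* = 0.1438 and 0.2154).

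- *K* is 5.93% in both arms.
- *C* = 0.0306/0.1744 × [1 − exp(−0.3488)] = 5.16% in the first arm, and 0.0306/0.2460 × [1 − exp(−0.4920)] = 4.83% in the second.

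Under this model the log-rank test with deaths censored compares the event hazards and is not disturbed by the mortality difference. The cumulative incidences do differ, because more deaths leave fewer people to have the event. Both contrasts are legitimate, but they answer different questions.

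**Crude percentages.** These do not censor deaths and so avoid this bias. They do need complete follow-up. Protocol 7.3 and section 12 end follow-up after the one-year visit for randomized subjects who receive no valve, and Protocol 7.12 and section 12 allow for withdrawal and loss. At two years, keeping such subjects in the denominator understates risk, and dropping them selects the sample.

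**The case against.** The strongest objection is that the only readable text assigning a method to these endpoints is Protocol 11.7.4, and it assigns counts and percentages. SAP 2.2.3 is generic and lists no endpoint. Kaplan-Meier may never be applied to stroke or reintervention, and censoring at death is inferred. This stands: a reader might infer that the reported rates *are* overstated, but the documents support only that they *would be* where Kaplan-Meier with deaths censored is used.

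A reader might also infer that no difference is estimated at the named times anywhere in the plan. That cannot be shown. The primary endpoints have their own non-inferiority tests, and much of the analysis text (in SAP 2.3.1, from 2.7 to 2.11, in 2.12 and in Protocol 11.10) is wholly or partly blacked out. What can be said is that SAP 2.2.3 itself offers a whole-curve test and no estimate at a fixed time.

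A third tempting inference is that the log-rank comparison mixes event risk with mortality. The equal-hazard example shows that it does not: with deaths censored, the test is a valid comparison of cause-specific hazards.

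The absolute sizes are also modest. For a true 5%, the excess ranges from about 0.2 points (early events, 15% mortality) to 1.4 points (constant hazards, 40% mortality). For comparison, the standard error of a difference between two 5% rates with 375 per arm is √(2 × 0.05 × 0.95/375) = 1.6 points.

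What remains is that two estimators are open for the same endpoints, and neither is right for a non-fatal event at two years with both deaths and incomplete follow-up.

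**Conclusion.** The point holds in conditional form. SAP 2.2.3 does not distinguish fatal from non-fatal outcomes, and it is not reconciled with Protocol 11.7.4. If Kaplan-Meier with deaths censored is used for the four non-fatal endpoints at one or two years, one minus the estimate would overstate the absolute risk. The relative excess is about 8–15% at one year and 15–27% at two under constant hazards, and roughly 4–10% in the early-clustering cases worked above.

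These sizes rest on assumed mortality of 15–25% at one year and 25–40% at two, and on independent hazards. The direction needs only that some deaths occur and are censored.

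The matter is confined to descriptive endpoints. SAP 2.6 ties success to the primary endpoints, both of which include death. The tests under multiplicity control that are readable in SAP 2.11 (superiority on the primaries; aortic regurgitation, KCCQ and six-minute walk) include no non-fatal time-to-event endpoint.

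**What to change.** In SAP 2.2.3:

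- List the endpoints treated as time-to-event.
- Keep Kaplan-Meier for all-cause mortality and for death or disabling stroke.
- For disabling stroke, non-disabling stroke or TIA, atrial fibrillation, and reintervention for aortic insufficiency, at every named time from six months on, use the Aalen-Johansen cumulative incidence with death as the competing event.
- Report the Portico minus CAV difference in cumulative incidence with a 95% CI at each named time.
- The log-rank test may stay, described as a comparison of cause-specific hazards.

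Name the same estimator in Protocol 11.7.4 for these four endpoints.

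The cost is wording and a standard procedure. The rates will be slightly lower than Kaplan-Meier rates and less directly comparable with published Kaplan-Meier figures, which can be shown alongside. Aalen-Johansen still assumes that censoring by withdrawal, loss or the one-year exit of non-implanted subjects is uninformative, so the number censored before two years should be reported by arm.
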